### 3. PONENTE Long Term Follow Up Substudy objectives

The main objective of the PONENTE Long Term Follow Up Substudy is to retrospectively collect changes of OCS and other background asthma maintenance medications, in a real-world setting 12 to 18 months after completion of the main PONENTE study. Additionally, the substudy aims to further observe shifts in the AI status in patients who had Complete or Partial AI at the end of the PONENTE study and to further evaluate the GTI over time.

Observational Objectives:	Outcome Measures:
To observe real-world clinical management of OCS dose 12 to 18 months after completion of the main PONENTE study	

Patients who achieve 100% reduction in daily OCS dose from baseline* OCS dose to the end of the long term follow up substudy

Patients who achieve a daily OCS dose of <math>\leq 5</math> mg at the end of the long term follow up substudy

Patients who achieve <math>\geq 90\%</math>, <math>\geq 75\%</math>, <math>\geq 50\%</math> or <math>>0\%</math> OCS reduction from baseline* OCS dose to the end of the long term follow up substudy.

Change in daily OCS dose from baseline* to the end of the long term follow up substudy

To observe real-world clinical management of background maintenance asthma regimen	

Change in background asthma maintenance medication from EOT of PONENTE main study* to the end of the long term follow up substudy

Safety Objectives:	Outcome Measures:

To observe shift in AI status in patients who had Complete AI or Partial AI at the end of the PONENTE study
 
To observe asthma exacerbations in adult patients from the main PONENTE study to the long term follow up visit
 
To assess the safety and tolerability from the main PONENTE study to the long term follow up visit
	

Shifts in AI status and further OCS dose changes from the main PONENTE study to the long term follow up visit

Annualized asthma exacerbation rate

Percentage of patients without exacerbation

Adverse events / Serious adverse events

Laboratory parameters and vital signs

To evaluate corticosteroid toxicity from the main PONENTE study to the long term follow up visit • Glucocorticoid toxicity index

\*the PONENTE main study baseline

#### **4. Inclusion criteria**

For inclusion in the PONENTE Long Term Follow Up substudy, patients should fulfil the following criteria:

- a. Patients must have completed the PONENTE EOT visit.
- b. Written informed consent to participate in the observational PONENTE Long Term Follow Up

#### **5. Exclusion criteria**

Patients should not enter the PONENTE Long Term Follow Up if any of the following exclusion criteria are fulfilled:

- a. Concurrent enrolment in another interventional clinical trial
- b. AstraZeneca staff involved in the planning and/or conduct of the study
- c. Employees of the study site or any other individuals involved with the conduct of the study, or immediate family members of such individuals

## 6. Study Plan and timing of procedures

**Table 8 PONENTE Long Term Follow Up Substudy – Study plan: Enrolment to End of Study**

Assessment/Activity	Protocol section	Enrollment	Long Term Follow Up Period	Withdrawal	Unscheduled Visit
		PONENTE Long Term Follow Up Enrolment (after EOT procedures) a	PONENTE Long Term Follow Up Visit		
Written Informed consent for long term follow up substudy b	Appendix K: 2.1	X			
Medical History		X			
Review EOT Visit Assessments	Table 1	X			
Brief physical examination	5.2.5.2	N/A		X	X
Vital signs	5.2.6	N/A	X	X	X
Weight	5.3.1	N/A	X	X	
Serum chemistry	5.2.4	N/A	X	X	
Hematology	5.2.4	N/A	X	X	
Morning Cortisol testing c	5.2.4	N/A	X	X	
Glucocorticoid toxicity index	5.2.1.1	N/A	X	X	
Assessment of asthma exacerbations	5.2.2/5.2.3	N/A	X	X	X
Adverse events	6.1	N/A	X	X	X
Concomitant medication	7.8 / Appendix K: 7	N/A	X	X	X
OCS and asthma medications	Appendix K: 7	N/A	X	X	X

- a. Enrolment for the PONENTE Long Term Follow Up substudy can occur any time after all PONENTE EOT procedures are completed. Patients who have already completed EOT prior to the start of the PONENTE Long Term Follow Up substudy may be contacted for participation at any time up to 18 months after the EOT visit. Assessments labeled N/A are not applicable because they will be collected as a part of the PONENTE EOT visit.
- b. ICF for the PONENTE Long Term Follow Up substudy must be obtained any time from EOT of the main PONENTE study and prior to any activities of the PONENTE Long Term Follow Up visit
- c. Patients who have Complete AI or Partial AI at the end of the primary PONENTE study will undergo a morning cortisol test at the Long Term Follow Up visit. Patients with indeterminate results will return to the site within a week after the Long Term Follow Up visit to conduct an ACTH stimulation test.

## **7. Concomitant medication and other treatments**

The PONENTE Long Term Follow Up is observational only. There are no sponsor-provided investigational products, restrictions related to concomitant medications other than those detailed in Section 3.5, or restrictions on concurrent disease. Restrictions described in Section 7.8 do not apply in the PONENTE Long Term Follow Up.

Additionally, from the EOT visit of the main PONENTE study to the Long Term Follow Up visit, any changes in the maintenance asthma regimen are allowed, including reductions of maintenance OCS therapy as recommended in the GINA report.

Due to potential interactions with morning cortisol and ACTH stimulation testing, the restrictions on concomitant medications detailed in Section 3.5 remain in place for the PONENTE Long Term Follow Up substudy.

## **8. Statistical Analyses by AstraZeneca**

### **8.1 Statistical Analysis Plan**

The PONENTE Long Term Follow Up will be managed under a separate SAP from the PONENTE main study and reported by way of an addendum to the PONENTE CSR.

### **8.2 Sample Size Estimate for PONENTE Long Term Follow Up substudy**

The PONENTE Long Term Follow Up is not formally powered; all patients from the PONENTE main study meeting all inclusion criteria and no exclusion criteria of this long term follow up substudy will be eligible to enrol.

### **8.3 Definition of analysis sets for PONENTE Long Term Follow Up substudy**

Observational and safety analyses will use a common analysis set – the Long Term Follow Up Analysis Set - which will include all patients who sign informed consent to continue into the PONENTE Long Term Follow Up . Two further analysis sets are defined as follows:

The "Biologic" Analysis Set will include all patients in the Long Term Follow Up Analysis set with  $\geq 50\%$  exposure to any biologic treatment for asthma during the PONENTE Long Term Follow Up ; and

The "Benralizumab" Analysis Set will include all patients in the Long Term Follow Up Analysis set with  $\geq 50\%$  exposure to commercial Benralizumab during the PONENTE Long Term Follow Up.

Additional analysis sets may be defined in the SAP.

### **8.4 Outcome measures for the PONENTE Long Term Follow Up substudy**

#### **Definition of baseline**

Baseline definitions will be as per definitions for the PONENTE main study (see the main PONENTE SAP for full definitions).

### **Outcome variables**

- Patients who achieve 100% reduction in daily OCS dose from PONENTE baseline dose to the Long Term Follow Up visit
- Patients who achieve a daily OCS dose of  $\leq 5$ mg (prednisone equivalent dose) at the Long Term Follow Up visit
- Patients who achieve  $\geq 90\%$ ,  $\geq 75\%$ ,  $\geq 50\%$  and  $> 0\%$  reduction in daily OCS dose from PONENTE baseline dose to the Long Term Follow Up visit
- Change in daily OCS dose (mg prednisone equivalent dose) from the baseline dose of the PONENTE main study to the Long Term Follow Up visit
- Change in background asthma maintenance medication from baseline of the PONENTE main study to the Long Term Follow Up visit

Change from baseline will be calculated as the post-baseline assessment value minus the baseline assessment value. If either value is missing, then the change from baseline value will be missing. Full details will be defined in the PONENTE Long Term Follow Up substudy SAP.

### **Safety outcome variables**

- Patients with complete AI and changes in AI status
- Annualized asthma exacerbation rate
- AEs, SAEs
- Laboratory parameters and vital signs
- GTI

## **8.5 Methods for statistical analyses for the PONENTE Long Term Follow Up substudy**

Statistical tabulation will be presented for all patients in the long term follow up analysis set, biologic analysis set and Benralizumab analysis set. Continuous variables will be summarized using the mean, two-sided 95% CI of the mean, the standard deviation, median, minimum value, and maximum value. Categorical variables will be summarized using frequency counts and percentages, as well as a two-sided 95% CI for proportions computed using exact Clopper-Pearson method. Data will be listed in patient-level data listings.

No formal hypothesis will be tested and no multiplicity adjustment will be applied in the statistical analysis. No imputation of observational or safety data will be performed. Imputation for partial dates will be detailed in the SAP.

### **Analysis of the observational variables**

Changes in OCS dose over time will be summarized using descriptive statistics in tables and presented graphically for the long term follow up analysis set, biologic analysis set and Benralizumab analysis set. Percentages achieving 100% reduction in OCS daily dose, a  $\leq 5$ mg daily dose, other pre-specified percentage reductions in OCS daily dose and reductions in background asthma medications will be reported with nominal 95% CIs derived using the exact Clopper-Pearson method.

Additional analyses will be detailed in the PONENTE Long Term Follow Up substudy SAP.

### **Analysis of safety outcomes**

The number and percentage of patients with complete AI at the Long Term Follow Up visit will be presented for the long term follow up analysis set, biologic analysis set and Benralizumab analysis set. A logistic regression model will be developed to identify factors potentially predictive of long-term adrenal insufficiency. Complete AI status at the Long Term Follow Up visit will be the dichotomous response variable with demographic, respiratory and metabolic baseline characteristics as explanatory variables. Full details will be provided in the SAP.

Spaghetti plots will be produced for patients in the long term follow up analysis set, biologic analysis set and Benralizumab analysis set with partial AI throughout the OCS reduction phase of the main PONENTE study, showing cortisol levels over time until the Long Term Follow Up visit.

The incidence of AEs and SAEs will be summarized over the PONENTE Long Term Follow Up substudy for comparison with incidence rates during the PONENTE main study. Summaries of laboratory parameters and vital signs may be provided, including absolute values and changes over time. Full details will be provided in the SAP.

The annualized rate of asthma exacerbations during the PONENTE Long Term Follow Up substudy will be summarized using mean, 95% CI and dispersion based on the negative binomial distribution, for the long term follow up analysis set, biologic analysis set and Benralizumab analysis set. This will be repeated for exacerbations resulting in hospitalization or an ER visit. Rates will be compared with those recorded during the PONENTE main study. The number and percentage of patients remaining exacerbation-free during the PONENTE Long Term Follow Up substudy will be presented.

Glucocorticoid toxicity index will be summarized over time from the start of the PONENTE main study to the end of the PONENTE Long Term Follow Up substudy, for the long term follow up analysis set, biologic analysis set and Benralizumab analysis set. Statistical correlation between GTI and daily OCS dose will be explored.

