### 2. PONENTE Long Term Follow Up Substudy Design

After completion of the EOT visit procedures, eligible patients (See Appendix K – Section [4](#) and [5](#)) may consent to a long term follow up visit 12 to 18 months after completion of the main PONENTE study. Accordingly, the long term follow up visit can occur in a range of 12 to 18 months after an eligible patient completes the EOT visit such that the last visit of the PONENTE Long Term Follow Up will take place 1-year after the last patient completes the EOT of the main PONENTE study.

Patients will be treated according to healthcare provider discretion and therefore no IP (i.e. Benralizumab) will be provided by the sponsor. Between the EOT visit of the main PONENTE study and the Long Term Follow Up visit, any changes in the maintenance asthma regimen are allowed, including further reductions of OCS as recommended in the GINA report ([GINA 2020](#)).

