3.3 Safety variables

Safety variables include:

- Disposition of adrenal function by morning cortisol and/or ACTH test
- Annualised asthma exacerbation rate and number (and percent) of patients with 0, 1, 2, etc exacerbations.
- Annualised asthma exacerbation rate leading to hospitalization or emergency room visit and number (and percent) of patients with 0,1, 2, etc exacerbations leading to hospitalization or emergency room visit
- AEs and SAEs
- Laboratory parameters
- Vital signs

- GTI

Safety analyses will use all available data, including data from unscheduled visits and repeated measurements.

[figure not shown]
Change from baseline to each post-treatment time point where scheduled assessments were made will be calculated for relevant measurements. Adverse events will be summarised by means of descriptive statistics and qualitative summaries.

No safety data will be imputed. The handling of partial/missing dates is detailed in Appendix 8.1.

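### Appendix K reports the substudy exacerbation-free percentage as a crude proportion, although follow-up runs from 12 to 18 months and patients may withdraw earlier; a fixed 12-month estimate is needed.

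*Protocol*

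**What the plan says.** Protocol Appendix K, section 3, lists "Percentage of patients without exacerbation" among the substudy's safety outcome measures, with no time point attached. Section 8.5, under the analysis of safety outcomes, repeats the measure: "The number and percentage of patients remaining exacerbation-free during the PONENTE Long Term Follow Up substudy will be presented". The general method in section 8.5 is: "Categorical variables will be summarized using frequency counts and percentages, as well as a two-sided 95% CI for proportions computed using exact Clopper-Pearson method". The same section adds: "No imputation of observational or safety data will be performed". No time-to-event method is named for the substudy.

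Follow-up is not of one length. Appendix K, section 2, says that "the long term follow up visit can occur in a range of 12 to 18 months after an eligible patient completes the EOT visit", and Table 8 provides a withdrawal column for patients who leave before that visit.

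Three analysis sets are defined in Appendix K, section 8.3. The common set for observational and safety analyses is everyone who consents. Two further sets require at least 50% exposure, either to any asthma biologic or, for the Benralizumab set, "exposure to commercial Benralizumab during the PONENTE Long Term Follow Up". Section 8.5 tabulates all three and also gives an annualized exacerbation rate based on the negative binomial distribution in each. Further detail is left to a separate substudy SAP, and the main SAP (sections 2, 3 and 4) refers to an addendum. Neither is among the documents reviewed.

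**The concern.** The chance of remaining free of exacerbation falls as the time observed grows. A percentage taken over windows of 12 to 18 months, some cut shorter by withdrawal, mixes probabilities that belong to different horizons. It answers neither how many patients were free at one year nor how many at eighteen months. Two groups with the same risk would show different percentages if one was seen later.

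At stake is the readability of one durability figure. A reader will probably take it as a one-year result, and may set it beside figures from elsewhere that have a fixed horizon. The Clopper-Pearson interval does not help: it describes sampling error around a quantity that has no defined time point.

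The start of the window is also open. Appendix K, section 2, counts the visit from EOT, while section 2.4 divides safety reporting at the main-study follow-up visit and at substudy consent. Section 8.5 does not say which date opens the exacerbation count.

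**Working it through.** The plan states no expected exacerbation rate, dispersion, sample size or power for the substudy, so there is no figure of its own to reproduce. The rates below are assumptions, shown over a range.

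**Inputs from the documents.** Follow-up of 1.0 to 1.5 years after EOT (Appendix K, section 2); a crude percentage with an exact interval (section 8.5); withdrawal possible before the visit (Table 8).

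**Assumptions.** Constant mean rate r = 0.6 per year; either Poisson events or negative binomial events with dispersion k = 1; follow-up uniform over 1.0 to 1.5 years.

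**Step 1: probability of no exacerbation by a fixed time t.**
- Poisson, exp(−rt): at 12 months exp(−0.6) = 54.9%; at 18 months exp(−0.9) = 40.7%.
- Negative binomial with k = 1, 1/(1 + rt): at 12 months 1/1.6 = 62.5%; at 18 months 1/1.9 = 52.6%.

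**Step 2: what the crude percentage would estimate.** Average step 1 over t from 1.0 to 1.5.
- Poisson: [exp(−0.6) − exp(−0.9)] / (0.6 × 0.5) = (0.5488 − 0.4066)/0.3 = 47.4%. This is 54.9 − 47.4 = 7.5 points below the 12-month value.
- Negative binomial: ln(1.9/1.6) / (0.6 × 0.5) = 0.1719/0.3 = 57.3%. This is 62.5 − 57.3 = 5.2 points below.

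**Step 3: other rates.** For r from 0.25 to 1.5 per year and k from 0 to 2, the mixed percentage lies 3.1 to 7.8 points below the 12-month value, with no change in risk.

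**Step 4: early withdrawal acts the other way.** In a simulation at 0.5 per year, 10% of patients withdraw before 12 months and count as exacerbation-free if no event was seen.

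| Model | Crude, no withdrawal | Crude, 10% withdraw | True at 12 months | Kaplan-Meier at 12 months |
|---|---|---|---|---|
| Poisson | 53.6% | 56.1% | 60.6% | 60.6% |
| Negative binomial, k = 1 | 61.7% | 63.7% | 66.8% | 66.7% to 66.8% |

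The crude figure moves with both visit timing and withdrawal. The Kaplan-Meier estimate recovers the 12-month value in each case.

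**Step 5: the exposure sets.** A second simulation gave the biologic no effect on risk (0.5 per year, k = 1, background stopping 0.2 per year). If 0%, 10%, 25% or 50% of patients stop after a first exacerbation, the set with at least 50% exposure shows 61.8%, 63.2%, 65.7% or 70.0% exacerbation-free, against about 61.7% in all patients. The documents give no stopping pattern, so this shows a direction and not an expected size. Across these runs and a parallel set at 1.0 per year, 12% to 21% of the set were off the biologic at the visit.

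**The case against.** The strongest reply is that a measure adjusted for time is already planned. The annualized rate is given in all three sets, and it is the rates, not the percentage, that section 8.5 compares with the main study. The percentage is an added descriptive line in an observational substudy that is not powered and tests no hypothesis. The spread in follow-up looks largely administrative, because Appendix K, section 2, closes the substudy one year after the last patient's EOT. The substudy SAP might also add a fixed-time estimate. All of this limits the harm. It does not repair the percentage, because the method Appendix K states for it has no horizon.

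Some stronger readings are tempting, but the documents do not support them.
- A reader might infer that the Biologic and Benralizumab sets keep only patients who stayed on treatment. The rule is at least 50% exposure, so a patient may start late or stop after half the period and still qualify.
- A reader might infer that the substudy results as a whole are conditioned on events after EOT. The common set is everyone who consents. A patient switched off benralizumab stays in it with every exacerbation and dose change. Unequal follow-up is variable observation time, which is a different matter from selection.
- A reader might carry the point to the main-study table, where SAP section 3.3 plans the "number (and percent) of patients with 0, 1, 2, etc exacerbations". The SAP pairs those counts with time-based rates, and section 3.3.2 gives the rates for separate study periods. The protocol synopsis puts an uncomplicated course at about 32 to 48 weeks and gives no wider range from which to size a problem.

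**Conclusion.** The point holds for the substudy's exacerbation-free percentage as Appendix K defines it. At the assumed 0.6 per year with uniform follow-up, the crude figure sits about 5 to 8 points below the 12-month value: 57% against 63% with dispersion 1, and 47% against 55% under Poisson. Comparing every patient at 12 months with every patient at 18 would suggest 10 to 14 points, but that contrast overstates the effect of a realistic mix. The size rests on an assumed rate, dispersion and visit spread; the direction needs only that exacerbations continue to occur after 12 months. Early withdrawal can offset part of it.

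For the two exposure sets the conclusion is narrower. Membership depends on treatment after EOT, so their results could look favourable if stopping follows an exacerbation. They are supplementary and are shown beside the set of all consenting patients, which makes this a matter of labelling. Overall this is an inexpensive improvement to a descriptive output and does not threaten the substudy's conclusions.

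**What to change.** In the substudy SAP:

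1. State the date on which exacerbation follow-up starts, either EOT or the main-study follow-up visit. The two are about 4 weeks apart (8 and 12 weeks after the last dose). Starting at EOT gives every patient who attends within the planned range at least 12 months, but those 4 weeks already count in the main study's on-study period (SAP section 3.3.2). Starting at the follow-up visit avoids the overlap, but leaves the earliest attenders slightly short of 12 months.
2. Report the Kaplan-Meier exacerbation-free proportion at 12 months with a 95% CI, censoring at withdrawal or at the long-term visit, in place of or beside the crude percentage. The sponsor already plans this kind of estimate for first OCS increase (SAP section 4.2.6.2).
3. Label results in the Biologic and Benralizumab sets as descriptive and print them beside the set of all consenting patients. Redefining the sets is optional. A rule based on the regimen started soon after the last study dose would answer a different question, need an arbitrary cut-off and still be decided partly after EOT.

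The cost is analysis wording. Exacerbations are already collected at the visit (Table 8), and the estimate needs their onset dates; Appendix K, section 8.5, already leaves partial dates to the SAP. The downside is that events after 12 months do not enter the estimate, although they remain in the annualized rate.

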### **Subgroup analysis**

Any subgroup analyses will be defined in the PONENTE Long Term Follow Up SAP.

## **9. Study timetable and end-of-study**

Enrolment for the PONENTE Long Term Follow Up substudy will be closed once the final PONENTE patient completes the EOT visit. For patients who participate in the PONENTE Long Term Follow Up substudy, the final study visit will be the Long Term Follow Up visit except for patients with indeterminate morning cortisol results at this visit who will return within 1 week after Long Term Follow Up visit to conduct the ACTH stimulation test.

## **Appendix L: Changes Related to Mitigation of Study Disruptions Due to Cases of Civil Crisis, Natural Disaster, or Public Health Crisis**

**Note:** Changes below should be implemented only during study disruptions due to any of or a combination of civil crisis, natural disaster, or public health crisis (eg, during quarantines and resulting site closures, regional travel restrictions and considerations if site personnel or study patients become infected with SARS-CoV-2 or similar pandemic infection) during which patients may not wish to or may be unable to visit the study site for study visits. These changes should only be implemented if allowable by local/regional guidelines and following agreement from the Sponsor and instructions on how to perform these procedures will be provided at the time of implementation.

Please note that during civil crisis, natural disaster, or public health crisis, some study assessments and procedures may not be conducted due to international or local policies or guidelines, hospital or clinic restrictions and other measures implemented to ensure the patient's safety. If in doubt, please contact the AZ Study Physician.

